4.4 Exclusion criteria

Patients meeting any of the following exclusion criteria are not eligible for enrollment:

- Evidence of distant metastases on any staging or imaging modality
- Women who are breast feeding, or have a positive pregnancy test (reproductive age should use effective birth control during study if randomized to SBRT treatment arm)
- Any patient with gross residual disease following salvage surgery
- Any co-morbidity or condition of sufficient severity to limit full compliance with the protocol per assessment by the principal investigator.

4.4.1 Specific criteria to exclude pregnant females and feta/neonatal exposure

For all females who are not at least one year post-menopausal or who have not undergone a surgical sterilization procedure, a urine pregnancy test will be done. If this is positive or questionable a serum pregnancy test will be done. The results of the pregnancy test must be negative in order for the patient to participate in this study.

Women who are pregnant or breastfeeding are excluded from participation in this study. All females of childbearing potential must have a serum pregnancy test within 14 days of the radiation. The results of the pregnancy test must be negative for the patient to participate in this study.

Subjects will be informed by the study staff that is extremely important that they not become pregnant or father a baby while participating in this study, and that avoiding sexual activity is the only certain method of preventing pregnancy. However, if a subject chooses to be sexually active, he or she must agree to use an appropriate "double barrier" method of birth control starting from the subject's participation in the screening process to include a negative pregnancy test to continue as a study participant and continuing until two weeks following the subject's participation in the study. The methods of birth control should include intrauterine device (IUD), contraceptive sponge and spermicide, in addition to male use of a condom, or the female should be using prescribed birth control implant. Subjects will be instructed to notify the study doctor of their birth control method prior to the start of the study, and also if they plan to change their birth control method.

Subjects that choose to be sexually active must be made aware that even with the use of birth control measures, pregnancy could still result. Subjects will be informed that if they become pregnant or impregnate a woman while taking part in this study, they must immediately notify one of the doctors listed on the consent form.

The information listed above will be relayed to applicable subjects by the study staff. It will also be listed in the consent form, a copy of which will be provided to the patients for them to take home.

5.0 TREATMENT EVALUATION, ADMINISTRATION, AND MODIFICATION

5.1 Primary outcome variables to be evaluated

- (1) Primary endpoint - local progression-free survival (LPFS), defined as the time from the date of randomization to the date of local progression or the date of death from any cause. Subjects who are alive and have not progressed will be censored at their last follow-up date.
- (2) Regional PFS, distant PFS, PFS (local + regional + distant): The definition of these endpoints is similar to LPFS.
- (3) Overall Survival: time from the date of randomization to the date of death due to any cause.
- (4) Acute and late toxicities of adjuvant SBRT. Acute toxicity is defined as toxicity occurring within 3 months of completion of SBRT. Late toxicity is defined as toxicity occurring later than 3 months after SBRT treatment.

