1.2 Adjuvant Re-Irradiation

The only phase III experience evaluating adjuvant therapy after surgical salvage is from the Institute Gustave-Roussy (7). In this phase III study, 130 previously-irradiated rHNC patients were randomized following salvage surgery to chemotherapy + re-irradiation (CT/Re-RT) versus observation. Chemotherapy consisted of six cycles of hydroxyurea and continuous infusion 5-FU, while adjuvant re-irradiation was delivered to a total dose of 60 Gy in a split-course fashion (the contemporaneous RTOG standard). Disease-free survival (DFS), but not overall survival (OS), was improved with the addition of adjuvant CT/Re-RT (the study was not powered for OS). However, this treatment was not without toxicity. Grade 3 or 4 mucositis was seen in 28% of patients and 39% of patients had grade 3 or 4 late toxicity versus only 10% of patients in the observation arm. This is the only level I evidence for adjuvant therapy in re-irradiation setting. Thus the data supports the role of re-irradiation in improving local control albeit with the expense of significant toxicity.

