2.0 OBJECTIVES

Primary

- 2.1 To compare the 1-year local control in patients with operable, recurrent previously-irradiated squamous cell head-and-neck cancers with or without adjuvant SBRT.

Secondary

- 2.2 To determine the locoregional progression-free survival (PFS) distant PFS, overall PFS (local + regional + distant), and overall survival (OS).
- 2.3 To evaluate the acute and late toxicities of adjuvant SBRT in the re-irradiation setting following salvage surgery.
- 2.4 To determine prognostic factors that may predict the likelihood of local failure, regional failure, or OS in this cohort to guide future management.
- 2.5 To compare the impact of adjuvant SBRT versus a wait-and-see approach on patient reported quality of life (PR-QoL).

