3.6.4 Follow-up/Long-term follow-up/Extended long-term follow-up procedures

Follow-up evaluations will be completed in patients in both arms (SBRT and wait-and see). They will be carefully followed every 3-6 months for 24 months or until death. Evaluations will consist of the following:

- Interim medical history and physical examination
- Careful documentation of Toxicity According to National Cancer Institute Common Toxicity Criteria Events Scale version 4.0
- Follow-up Patient-Reported Quality of Life Assessment (PR-QoL)
- FDG PET-CT at 8-12 weeks post-treatment then every 12 weeks

TABLE 1: Treatment Schema

		Clinical Visit			
Assessment		Pre-Study	During 8-12 weeks	Q 12-24 weeks	SBRT Post for 2-years
	History + Physical	X	X	X	X
	Imaging	X	X	X	
	QoL Assessment	X	X	X	

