6.4 Analysis of primary and secondary endpoints

Survival endpoints will be estimated by the Kaplan-Meier method and the corresponding median survival times (with 95% confidence interval) reported. The one-year LPFS will also be estimated along with its 95% confidence interval. Survival will be compared between the two arms with the one-sided log-rank test. Effect of treatment and other variables (e.g., baseline characteristics, biomarkers etc) on survival will be explored with Cox regression models.

For the quality of life (QoL) data analysis, each item of the UW-QoL-R will be individually assessed. The mean and standard deviation of the observed data will be summarized at each collection time and plotted against time, from baseline through the end of patient follow-up. Generalized linear models (such as cumulative logit models) for repeated measures will be used to explore if there are significant changes in PR-QOL over time.

Using NCI Common Terminology Criteria for Adverse Events (CTCAE v4.0), the number of patients experiencing adverse events over their course of treatment will be characterized by type of adverse event and grade, by the time of onset in relation to the first day of therapy, and whether the event is clinically significant. Attribution of adverse events to treatment (unrelated, unlikely, possibly, probably, or definitely) will also be summarized for any serious adverse events (SAEs), CTCAE grade 3 or higher. The percentage of patients experiencing SAEs that are considered to be treatment-related (probable or definite) will be determined. The percentages of patients experiencing the acute/late toxicities associated with SBRT will also be estimated along with their exact 95% confidence intervals.

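### Acute and late toxicity are timed only from SBRT, so control-arm toxicity cannot be classed as acute or late and no between-arm estimate is planned

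*Combined protocol and SAP*

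**What the plan says.** Section 5.1(4) sets both toxicity windows by SBRT: "Acute toxicity is defined as toxicity occurring within 3 months of completion of SBRT", and "Late toxicity is defined as toxicity occurring later than 3 months after SBRT treatment". The efficacy endpoints in the same section start from a date that every patient has. LPFS is "defined as the time from the date of randomization to the date of local progression or the date of death from any cause", and OS also starts at randomization.

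Section 6.4 describes adverse events by type, by grade and "by the time of onset in relation to the first day of therapy". It summarises attribution for serious events of grade 3 or higher. It plans exact 95% intervals for acute and late percentages, but only for toxicities linked to SBRT. Section 6.3 analyses safety by treatment actually received. No difference in toxicity between the arms is planned anywhere.

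On data collection, 3.6.4 states "Follow-up evaluations will be completed in patients in both arms (SBRT and wait-and see", and CTCAE v4.0 toxicity is among the listed evaluations. The toxicity objective (2.3) reads "To evaluate the acute and late toxicities of adjuvant SBRT in the re-irradiation setting following salvage surgery". The quality-of-life objective (2.5), by contrast, reads "To compare the impact of adjuvant SBRT versus a wait-and-see approach on patient reported quality of life (PR-QoL".

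**The concern.** A wait-and-see patient has no SBRT date. Nor is a first day of therapy defined for that patient, unless the discretionary systemic therapy allowed in 4.3 is meant to count. Followed as written, the plan collects control-arm toxicity and then has no rule for calling it acute or late.

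This matters because the background event rate is unlikely to be negligible. Every patient has had salvage surgery in a previously irradiated field with high-risk features (4.1), and either arm may receive systemic therapy (4.3). The protocol's own background judges the cost of re-irradiation by a randomized contrast: "39% of patients had grade 3 or 4 late toxicity versus only 10% of patients in the observation arm" (1.2). Section 1.4 then puts forward reduced toxicity as part of the case for SBRT. The analysis plan leaves out the kind of comparison that this reasoning relies on, although the trial has a randomized control arm.

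**Working it through.** **1. The plan's own figure.** The only sample size stated is 21 per arm for LPFS (6.2); none is given for toxicity.
- Hazard ratio under constant hazards: ln(0.52)/ln(0.20) = 0.406.
- Schoenfeld events at one-sided 0.10 and 90% power: 4 × (1.282 + 1.282)² / (ln 0.406)² = 32.4, rounded up to 33.
- Event probability with 2 years' uniform accrual and 1 further year: 1 − (e^(−λ) − e^(−3λ))/(2λ). This gives 0.940 for control and 0.710 for SBRT, mean 0.825.
- N = 33/0.825 = 40.0, or 20.0 per arm; 20.0/0.95 = 21.05. Treating loss as 5% per year gives 20.7.

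The stated 21 reproduces. It is used below only as the number available for a toxicity contrast.

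**2. The clocks side by side.**

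| Item | Counted from | SBRT arm | Wait-and-see arm |
|---|---|---|---|
| LPFS, OS (5.1) | randomization | defined | defined |
| Acute toxicity (5.1) | SBRT completion | defined | no date |
| Late toxicity (5.1) | SBRT | defined | no date |
| Onset of adverse events (6.4) | first day of therapy | defined | not defined |
| Type and grade (6.4) | none needed | available | available |

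The 5.1 and 6.4 toxicity clocks also differ from each other. Section 5.1 does not say how events during the 1-2 weeks of SBRT are classed.

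**3. Where the existing boundary falls.** Section 3.6.3.2 has SBRT completed 4 to 12 weeks after surgery. Taking 3 months as 13 weeks, the acute/late boundary in SBRT patients lies between 4 + 13 = 17 and 12 + 13 = 25 weeks after surgery.

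**4. What a between-arm estimate would deliver.** The 39% and 10% in 1.2 come from 60 Gy split-course re-irradiation with chemotherapy against observation. They are an illustration, not assumptions of this trial.
- SE of the difference: √(0.39×0.61/21 + 0.10×0.90/21) = 0.125.
- Nearest whole counts: 8/21 (exact 95% CI 18% to 62%) and 2/21 (1% to 30%).
- Difference 6/21 = 29 points; Newcombe 95% CI 3 to 51.
- Power at 39% versus 10%: about 59% at two-sided 0.05 and 83% at one-sided 0.10.

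With a smaller excess, 20% versus 10% (my assumption), the SE is √(0.20×0.80/21 + 0.10×0.90/21) = 0.109. The Wald 95% CI is 10 ± 21 points, about −11 to 31.

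**5. Time at risk.** Section 6.2 assumes one-year LPFS of 20% and 52%, so 80% of controls and 48% of SBRT patients are expected to have progressed locally or died by one year. Under the same constant hazards, six-month LPFS is √0.20 = 45% and √0.52 = 72%. By about the time late toxicity starts to count, 55% of controls and 28% of SBRT patients would have had an LPFS event. The documents do not split these into deaths and progressions. A crude late-toxicity percentage would still compare arms with unequal time at risk.

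**The case against.** The strongest reply is that the plan answers the objective it set. Objective 2.3 asks to evaluate SBRT toxicity, while 2.5 asks to compare quality of life. An SBRT-arm percentage with an exact interval, supported by attribution of serious events of grade 3 or higher, is a recognised way to do that. This stands as far as it goes: a between-arm estimate extends the written objective. But saying which toxicities belong to SBRT means separating them from background. Attribution does this case by case, no blinding is described, and lower-grade events are not covered.

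A reader might infer that the trial cannot use its control arm for safety at all. The documents do not support that. Toxicity is collected in both arms, the safety set does not exclude controls, tables by type and grade need no SBRT date, and every patient has a randomization date.

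A reader might also take 10 of 39 points from 1.2 and conclude that a quarter of reported toxicity would be wrongly charged to SBRT. That does not follow. The rates belong to a different regimen, 1.4 expects SBRT to be less toxic than conventional re-irradiation, and the inference ignores attribution.

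Nor are patients who stop SBRT early clearly outside both windows: the late window runs from SBRT treatment, not its completion. For events during SBRT, 6.4 covers the course of treatment, so this is a matter of wording.

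Finally, the contrast is imprecise, and early ascertainment may differ by arm. Sections 3.5 and 3.6.4 count the first follow-up from treatment, and no control contact matching the SBRT weeks is specified. Both points stand, and they argue for a descriptive analysis with that caveat stated.

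**Conclusion.** The gap is one of definition and analysis. As written, control-arm toxicity cannot be classed as acute or late, no between-arm toxicity estimate is planned, and objective 2.3 rests on an SBRT-only rate plus attribution. A by-arm estimate on a common clock is a better answer at small cost.

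Its likely precision is low. The 95% CI is about 3 to 51 points at the illustrative 39% versus 10%, and about −11 to 31 at an assumed 20% versus 10%. Both assume that all 21 patients per arm are evaluable, which is optimistic for late toxicity given the expected progression and death. The point concerns a secondary objective and leaves the primary analysis and the 21 per arm untouched.

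**What to change.** In 5.1(4):
- Add one clock for both arms that counts only events after randomization, the origin 5.1 already gives for LPFS and OS. Counting every event from surgery would bring in morbidity from before randomization, since enrollment follows surgery and final pathology (4.3). Section 3.6.6 measures survival from surgery and should be reconciled with 5.1 as well.
- Set one fixed acute/late boundary for both arms, for example 12 weeks plus 3 months after salvage surgery, taken from the completion limit in 3.6.3.2.
- State that events during SBRT are classed as acute.

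In 6.4:
- Report each arm's percentage by type and grade, and the between-arm difference with a 95% CI, regardless of attribution and labelled descriptive. If any patient's treatment differs from the assignment, show the table by assignment as well as by treatment received.
- For late toxicity, also account for time at risk, for example by cumulative incidence with death as a competing event.
- Keep the SBRT-anchored windows and the attribution summaries as supplementary, and reconcile the onset clock with 5.1.

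The cost is revised wording and one extra table, with no additional patients. Some SBRT-arm events move from late to acute. With the example boundary at about 25 weeks after surgery, a patient who completes SBRT at week 4 has the boundary moved by 25 − 17 = 8 weeks; one who completes at week 12 sees no change. The revised text should therefore say that acute counts will not match the SBRT-anchored ones.

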3.6 Research Activities

3.6.1 Pretreatment Evaluation

The following tests/procedures will be performed within 3 months prior to registration unless otherwise specified:

- Medical history and physical examination
- Pathologic confirmation of diagnosis and disease status/staging with biopsy to rule out metastatic disease if necessary
- Baseline laboratory assessment, including CBC and blood chemistry

- Urine or blood β -HCG within 14 days prior to study start for females who are not at least one year post-menopausal or who have not undergone a surgical sterilization procedure
- CT (computed tomography) scan or FDG-PET-CT (^{18}F -fluorodeoxyglucose positron emission tomography/computed tomography) of the neck and chest
- Baseline Quality of Life Assessment (University of Washington – Quality of Life – Revised (UW-QoL-R)

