3.6.3.2 Randomized Arm

Patients randomized to the adjuvant SBRT arm will receive 40-50Gy in 5 fractions on non-consecutive days in 1-2 weeks on an outpatient basis. SBRT should be completed at a minimum of 4-weeks following salvage surgery, with a maximum of 12-weeks. CTV (clinical target volume) will represent the tumor bed/high-risk region as defined by head and neck surgeon and radiation oncologist. A maximum of 5mm expansion from CTV to PTV (planning target volume) shall be applied

Treatment Volumes $< 25\text{cc}$ will receive 40Gy (5 fractions of 8 Gy per fraction)
 Treatment Volumes $\geq 25\text{cc}$ will receive 44-50Gy over 5 fractions (5 fractions of 8.8Gy per fraction). Ideally, all tumors volumes $\geq 25\text{cc}$ will receive 50Gy over 5 fractions; however, at the discretion of the treating radiation oncologist based on tumor volume, prior radiation dose and proximity to critical organs, the dose can be reduced to 44Gy over 5 fractions as outlined in prior SBRT protocols.

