4.3 Inclusion criteria

Each patient must meet all of the following inclusion criteria for study enrollment:

- Age ≥ 18 with ability to provide written informed consent
- Pathologically proven recurrent or second-primary head-and-neck cancer receiving prior radiotherapy with or without chemotherapy
- Prior radiotherapy to a dose of $\geq 50\text{Gy}$
- No evidence of distant metastases
- Macroscopic complete salvage surgery with curative intent (surgery was not performed only for biopsy or palliation). Final pathology and imaging must indicate a R0 or R1 resection (no gross disease remaining).
- High-risk pathologic features must be present: compromised/positive surgical margins ($\leq 2\text{mm}$) or extra-nodal extension (patient with other high-risk features gross perineural invasion, bone invasion, angiolytic invasion, or a constellation of these factors may be eligible based on case-by-case basis at discretion of principal investigator).
- Karnofsky Performance Status ≥ 60 (ECOG 0-2)

- Any number or type of prior chemotherapy is allowed (patient may receive concurrent or adjuvant systemic therapy such as cetuximab at the discretion of the treating oncologic team).

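### Acute and late SBRT toxicity are defined by time since SBRT, with no CTCAE grade between salvage surgery and randomization and no matching window for controls, so existing morbidity can be miscounted in either direction

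*Combined protocol and SAP*

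**What the plan says.** Section 5.1(4) names the endpoint as acute and late toxicities of adjuvant SBRT and then divides it by time: "Acute toxicity is defined as toxicity occurring within 3 months of completion of SBRT", and "Late toxicity is defined as toxicity occurring later than 3 months after SBRT treatment". Neither sentence mentions a pre-existing grade, new onset or worsening.

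The baseline lists in 3.2 and 3.6.1 cover history and examination, pathology, laboratory tests, a pregnancy test, imaging and the UW-QoL-R, but no CTCAE grading. Table 1 in 3.6.4 has no toxicity row. Visit-level grading appears in the follow-up list of 3.6.4, for both arms: "Careful documentation of Toxicity According to National Cancer Institute Common Toxicity Criteria Events Scale version 4.0". The Protocol Summary also names CTCAE v4.0, without saying when it is applied.

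On analysis, 6.4 states: "The percentages of patients experiencing the acute/late toxicities associated with SBRT will also be estimated along with their exact 95% confidence intervals". It also plans five-level attribution for serious adverse events of grade 3 or higher, a treatment-related percentage limited to probable or definite, and a description of events by onset relative to the start of therapy. Section 6.3 analyses safety by treatment received.

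On patients and timing, 4.3 requires at least 50 Gy of prior radiotherapy and salvage surgery, and 3.6.3.2 says "SBRT should be completed at a minimum of 4-weeks following salvage surgery, with a maximum of 12-weeks".

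**The concern.** Objective 2.3 is to evaluate the toxicity of adjuvant SBRT after salvage surgery. Patients who have been irradiated and recently operated on can be expected to arrive with some gradeable problems, such as dysphagia, pain or wound trouble. If those problems are first graded at follow-up, the analyst cannot tell carried-over morbidity from an event that is new or worse after SBRT.

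The resulting percentage will be read against the protocol's own benchmark. Section 1.4 argues that SBRT may be less toxic than conventional adjuvant re-irradiation, and 1.2 reports for the randomized study of chemotherapy plus re-irradiation that "39% of patients had grade 3 or 4 late toxicity versus only 10% of patients in the observation arm". A rate raised by existing morbidity could hide a real advantage. A rate lowered by ascribing true worsening to surgery could suggest one that is not there.

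**Working it through.** **1. The plan's own figure.** The documents state no toxicity rate or precision target. The only relevant figure is the denominator, 21 per arm (6.2), and it reproduces. With exponential survival, HR = ln(0.52)/ln(0.20) = 0.406. Schoenfeld events = 4 × (1.2816 + 1.2816)² / (ln 0.406)² = 32.4, so 33. With 2 years of accrual and 1 year of follow-up the average event probability is 0.825, so 33 / 0.825 / 2 = 20.0 per arm, and 20.0 / 0.95 = 21.05 after 5% loss. Sample size is not at issue.

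**2. When a grade exists.**
- SBRT ends 4-12 weeks after surgery (3.6.3.2), and 3.5 places the first follow-up 8-12 weeks after treatment. The first scheduled CTCAE grade in the SBRT arm therefore falls between 4 + 8 = 12 and 12 + 12 = 24 weeks after surgery.
- The 3.6.1 assessments may be done up to 3 months (about 13 weeks) before registration. Registration precedes the end of SBRT, so for a patient treated on schedule it falls less than 12 weeks after surgery. A 13-week look-back therefore always reaches to before surgery, and the required history and examination may be pre-operative.
- Three months is about 13 weeks, so the 8-12 week visit lies in the acute window and later visits in the late one. An unchanged problem could be graded in both.

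**3. What each safeguard in 6.4 needs.**
- Restriction to SBRT-associated toxicity: no rule for deciding association is given.
- Attribution: stated for serious events of grade 3 or higher, not below.
- Time of onset: needs the state before treatment, which is not graded.
- Control arm: followed for CTCAE toxicity, but both windows start at SBRT, a date controls do not have. No between-arm toxicity comparison is specified.

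**4. Size.** Let s be the true new-event rate, b the share entering with a persistent grade 3 or higher problem, independent of s. If nothing is filtered out, the counted rate is 1 − (1 − b)(1 − s). Take s = 10% (assumption). The values of b are also assumptions.

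| b | Counted rate | Excess (points) | Expected of 21 | Nearest count, exact 95% CI |
|---|---|---|---|---|
| 0% | 10% | 0 | 2.1 | 2/21: 1.2%-30.4% |
| 10% | 1 − 0.9 × 0.9 = 19% | 9 | 4.0 | 4/21: 5.4%-41.9% |
| 20% | 1 − 0.8 × 0.9 = 28% | 18 | 5.9 | 6/21: 11.3%-52.2% |
| 30% | 1 − 0.7 × 0.9 = 37% | 27 | 7.8 | 8/21: 18.1%-61.6% |

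Filtering lowers these figures: b = 30% with two thirds of carried-over cases removed equals b = 10% unfiltered, or 19%. Full and correct filtering returns 10%. If true worsening is put down to surgery, the counted rate can fall below 10%.

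**The case against.** The endpoint is not defined by time alone. The opening of 5.1(4) limits it to toxicity of SBRT, and the time sentences only split that category. Section 6.4 adds attribution and a probable/definite rate for serious events of grade 3 or higher, the very grade used in the illustration. Recording of onset would place a problem that began after surgery before treatment. A history and a baseline UW-QoL-R are required, and 7.1 has staff watching for adverse events throughout. The wait-and-see arm, formed by randomization and followed for CTCAE toxicity, shows the background. The endpoint is secondary and descriptive, and at 21 patients the intervals for 2/21 and 4/21 overlap heavily.

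Much of this stands. A reader might infer that surgical and radiation morbidity will necessarily enter the SBRT rate, or that 19-37% is the expected result. The documents support neither: the 6.4 safeguards would remove some carried-over cases, and error can run both ways. A reader might also take the 10% in 1.2 as an entry prevalence or as a rate in unirradiated patients. It is neither: those patients had been irradiated before, were not re-irradiated, and the 10% is late toxicity in follow-up.

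What does not stand is that the safeguards close the gap. Each relies on knowing the earlier state. The history may predate surgery, the UW-QoL-R is patient-reported and not a CTCAE grade, and the control arm cannot be set beside the SBRT arm without a shared window.

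**Conclusion.** The point holds as a gap in measurement and definition, not as a demonstrated bias. No CTCAE grade is scheduled between surgery and randomization, association with SBRT has no rule, attribution is not stated below grade 3, and controls have no matching window. The SBRT toxicity percentages can therefore be too high or too low, and the data would not show which.

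The 19-37% against a true 10% is an upper bound. It rests on an assumed 10% new-event rate, an assumed 10-30% entry prevalence, independence and no filtering. The documents give no baseline prevalence, so the actual size is unknown. The sample size and the primary analysis are unaffected. The change is worth making because it is cheap and a post-surgery, pre-randomization grade cannot be reliably rebuilt later.

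**What to change.** - **3.2, 3.6.1 and Table 1:** add CTCAE v4.0 grading in both arms at registration/randomization, after surgery and before the arm is known. Do not rely on the existing history and examination, which may predate surgery.
- **5.1(4) and 6.4:** count an acute or late event only if it is new or at least one grade worse than that baseline. State how association with SBRT is decided, and apply attribution to all acute and late events, including those below grade 3.
- **Between-arm summary:** use a common anchor such as randomization. This also helps with surgical complications that first appear after baseline, which a baseline grade alone cannot separate from SBRT effects. The SBRT-anchored split can stay for describing the SBRT arm.
- **Reporting:** give the baseline prevalence of grade 3 or higher morbidity by arm.

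Cost: one extra form per patient, a little data entry and short edits to the sections named. Sample size and primary analysis do not change.
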